B4. Chinese Americans, socio-cultural barriers and lifestyle-related stomach cancer risk factors. *Health care access.* For Chinese American communities, the risk of stomach cancer is compounded by difficulties in accessing healthcare services, and attendant linguistic, cultural, economic and social barriers, which contribute to delayed cancer screenings,²¹⁻²⁴ poor medication adherence, and poor disease self-management skills.²⁵⁻²⁸ *Acculturation* (which includes indicators such as nativity, years in the US, English language proficiency) is a significant factor that influences health access and behaviors for Chinese American immigrant communities, including impacting screening and disease prevention.^{25,26}

B5. Evidence-base for test-and-treat in high-risk Chinese populations.

The American College of Gastroenterology's 2017 clinical guidelines for treating *H. pylori* infection recommends clarithromycin triple therapy consisting of a proton pump inhibitor (PPI), clarithromycin, and amoxicillin or metronidazole for 14 days where *H. pylori* clarithromycin resistance is known to be <15%.²⁹ This is an oral regimen of 6-8 pills taken daily at different dosing intervals for 14 days. Test for treatment success of eradication therapy should occur at least 4 weeks after completion of antibiotics and with patients off PPI for 1-2 weeks, using urea breath test, fecal antigen test, endoscopic testing or other clinically approved *H. pylori* infection diagnostic test.

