CHW Components. We will refine the CHW protocol and curriculum. We will conduct a scan of CHW and/or care coordination efforts at the sites to determine possible leverage points for the placement of CHW initiatives or opportunities to support train-the-trainer models. The advisory group will also review any existing materials, adapt them culturally and linguistically for the target population, and integrate with the existing pilot CHW educational curriculum. The Ecological Validity Model⁷⁸ complemented by a social marketing approach⁷⁹ will be applied, to assess and adapt the materials. Small media materials will be produced by the advisory group using a participatory process, adapted from our previous studies,⁸⁰⁻⁸² and may include bilingual palm cards and pamphlets on *H. pylori* eradication therapy, side effects and stomach cancer prevention.

To enhance scientific rigor, measure selection was based on: 1) brevity; 2) presence of domains with face validity for Asian American or low-literacy communities; and 3) valid psychometric properties. The **primary outcome** measure is the most rigorous outcome measure related to *H. pylori* eradication: confirmation of *H. pylori* eradication by fecal antigen test or other clinically approved *H. pylori* infection diagnostic test conducted 4 weeks–3 months post-treatment (to be extracted from EHR). **Secondary outcomes** include: self-efficacy, health literacy, medication adherence and other factors. Medication adherence measured using simplified medication adherence questionnaire (SMAQ) and medication adherence report scale (MARS-5). Self-efficacy will be measured by the Ottawa Decision Self-Efficacy Scale. Health literacy will be assessed using the short form of the European Health Literacy Survey Questionnaire (HLS-EU-Q12). Health-related quality of life will be measured by the Patient-Reported Outcome Measurement Information System Global Health Scale (PROMIS).⁸⁶

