Inclusion Criteria: An individual is eligible for the intervention if s/he: a) self identifies as Chinese American; b) is an outpatient aged 21+; c) plans to continue to live in the region during the next 12 months; d) is willing to be randomized to either treatment or control groups; and e) has a confirmed diagnosis of *H. pylori* infection by at least one of the following methods: C-urea breath test, histology, rapid urease test or bacterial culture, fecal stool antigen test or other clinically approved *H. pylori* infection diagnostic test.⁹⁴

Exclusion Criteria: The exclusion criteria include: a) advanced chronic disease that would not allow the patient to complete follow-up or attend visits; b) allergy to any of the treatment drugs; c) previous gastric surgery; d) pregnancy or currently breastfeeding; e) taking antibiotics or bismuth salts within 2 weeks before the study.

Rationale for proposed exclusion of gender and racial/ethnic group members: Individuals from other racial/ethnic groups are excluded from participation in the intervention as this study is focused on Chinese American adults. Men and women will both be invited to participate in this intervention. No children or vulnerable subjects will be enrolled in this study.

Substudy

Inclusion criteria: An individual is eligible for the substudy if s/he is: a) enrolled in the EHR-CHW Intervention main study; and b) is willing to provide either an oral sample, a fecal sample, or both. Individuals will be excluded from the substudy if they are unable to mail the samples back to the study team.

Key Informant Interviews

Inclusion Criteria: Interviewees must be an adult (18 years and over) and they must be a provider, an administrator, or a community health worker. Individuals will be excluded from the interview if the interview cannot be conducted in the English language.

III. METHODS & PROCEDURES

A. Methods & Procedures

A1. EHR-CHW Intervention Components

EHR Component

Epic, the EHR system, has been integrated at NYU Langone Health, and is being implemented at Bellevue and Gouverneur Hospitals. [name] will oversee MCIT in creating the proposed EHR enhancements.

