CHW Intervention Components. The intervention arm protocol consists of 4 educational sessions: session 1 will focus on medication adherence, treatment side effects, and the link between *H. pylori* and stomach cancer; and sessions 2 through 4 will focus on reinforcing session 1 themes, stomach cancer risk reduction, and links to community-based resources. The sessions employ adult learning techniques and group-based learning activities. All session materials are culturally and linguistically adapted. The in-person sessions will be held at the clinics, community spaces identified by partner agencies or by telephone. These sessions will be accompanied by phone call, text or voicemail medication and follow-up reminders in the preferred language (frequency depending on participant preference). The intervention materials will model scripts and messages informed by Social Cognitive Theory and will include reviewing and reinforcing individualized challenges, strategies and action plans for medication adherence and stomach cancer prevention.

A2. Data Collection

The recruitment and data collection protocol will be finalized with substantial feedback from the advisory group. All study staff involved in recruitment and data collection will receive a standardized training orientation on administering surveys and will be certified in human subjects research via the Collaborative Institutional Training Initiative (CITI Program).

EHR data will be used for recruitment and for the determination of primary outcomes. [name] will work with MCIT to identify potential participants from EPIC databases. During the recruitment period, registry lists will be generated weekly from EHR for physicians who have approved participation of their patients. Patients will be contacted either by phone (up to 3 calls) or in person by CHW. All preliminary EHR data will be deleted or shredded after one week of retrieval. EHR data to be shared with the study team include: demographics (gender, age, race/ethnicity (if available), language (if available), diagnosis of *H. pylori* through ICD codes, dates of clinic visits, name, and telephone number. Scheduled office visits will be tracked via quarterly EHR data pulls. EHR data will also be used to follow-up with the

outcome of treatment regimens and to determine *H.pylori* eradication via fecal stool antigen tests based on treatment follow-up procedures of physicians.

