All analyses will be conducted using intention-to-treat methods to minimize the risk of attrition bias. The *primary analyses* of differences in *H. pylori* eradication between the intervention and usual care groups will first be tested using a chi-squared test of binomial proportions. We will assess level of participation for those randomized into the intervention arm, and explore whether level of participation is associated with greater changes in health outcomes. Logistic regression analysis will be used to analyze differences in outcome between those who receive the intervention and those who do not, controlling for potential confounding factors. All quantitative data will be entered and analyzed using standard statistical packages (e.g., SAS, R, Stata). The primary analysis will assume that any patient lost to follow-up failed to achieve *H. pylori* eradication. As a sensitivity analysis, we will apply multiple imputation to impute missing outcomes assuming a missing-at-random mechanism.

The analysis of *secondary outcomes* is guided in part by the Social Cognitive Theory. We hypothesize that the intervention group, when compared with usual care, will report: 1) increased medication adherence; 2) increased self-efficacy for adherence; 3) improved health literacy; 4) improved knowledge about stomach cancer prevention; and 5) higher levels of perceived health related quality of life. We will compare these intermediate outcomes between groups using t-test or its non-parametric equivalent, the Wilcoxon rank-sum test. Sex as a biological variable will be addressed by exploring gender as a potential moderator of intervention effects.

Power calculations. For the control group, we conservatively estimate that approximately 55% will achieve *H. pylori* eradication based on several studies of overall and, specifically, Chinese American populations.^{36,45,46,100} We wish to detect an increase in this rate to approximately 80% in the intervention group; this difference is reasonable based on studies in Ireland and China that showed increases of approximately this magnitude in rates of knowledge and high adherence in similar populations.^{36,44,45} Accrual of 144 participants, evenly randomized to intervention or usual care, provide greater than 80% power to detect this difference, using a 2-sided, 0.05-level test.

B1a. Substudy Data Analysis.

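### The outcome window starts at the end of treatment and no rule scores participants who never start, so the planned imputation could credit untreated patients with eradication

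*Combined protocol and SAP*

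**What the plan says.** - **Outcome and window** (Study Design, C2): the primary outcome is confirmation of eradication by a clinically approved test "conducted 4 weeks–3 months post-treatment", taken from the EHR. Background B5 uses the same anchor: the test "should occur at least 4 weeks after completion of antibiotics". No window is given from randomisation.
- **Who orders the test** (III.A2, Data Collection): eradication is determined from the EHR "based on treatment follow-up procedures of physicians", so it depends on routine care.
- **Eligibility** (II, Inclusion Criteria): the person "has a confirmed diagnosis of" *H. pylori* infection. No criterion requires that therapy has been prescribed or started. Registry recruitment looks for diagnoses made within the last 7 days (III.A1), so randomisation can come before treatment.
- **Analysis** (III.B1): "All analyses will be conducted using intention-to-treat methods to minimize the risk of attrition bias". The primary analysis "will assume that any patient lost to follow-up failed to achieve" eradication. As a sensitivity analysis, "we will apply multiple imputation to impute missing outcomes assuming a missing-at-random mechanism".

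The term for patients lost to follow-up is not defined, the variables in the imputation model are not named, and nothing says how a participant who never starts the course is scored.

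**The concern.** The window depends on an event after randomisation, and the intervention is meant to influence treatment-taking. A participant who never starts has no post-treatment period and little reason to be tested. If that person still completes the 2- and 6-month surveys, they are not lost in the ordinary sense, so the failure rule does not clearly reach them.

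The outcomes that are observed come almost entirely from treated people. An imputation model built on those outcomes would give a never-starter about the same chance of eradication as a treated patient in the same arm. The analysis meant to test the robustness of the primary result would then credit eradication to people who took no antibiotics, and its difference between arms would partly reflect how many never started in each.

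**Working it through.** **Step 1: the plan's own figure.** Inputs from III.B1: 55% against 80%, 144 participants (72 per arm), two-sided 0.05.

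Power = Φ[(0.25 − 1.96 × √(2 × 0.675 × 0.325 / 72)) / √((0.55 × 0.45 + 0.80 × 0.20) / 72)] = Φ[(0.25 − 0.153) / 0.0752] = Φ(1.29) = 90%.

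Exact enumeration of the uncorrected chi-squared test also gives 90%, and 87% with a continuity correction. The plan's claim of more than 80% reproduces.

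**Step 2: assumptions for the imputation.** The documents give no never-start rate, so a range is shown. I take 55% and 80% as the true rates over all randomised participants, with never-starters not eradicated. I also assume that never-starters are the only missing outcomes and that imputation is within arm without further covariates.

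**Step 3: formula.** If a share s of an arm never starts and is set to missing, every eradication lies in the remaining 1 − s. The expected imputed rate is therefore:

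imputed rate = true rate / (1 − s)

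Expected eradications imputed to untreated people = 72 × s × imputed rate.

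Example at 20% control and 10% intervention: 0.55/0.80 = 68.8% and 0.80/0.90 = 88.9%, a difference of 20.1 points. Imputed eradications: 72 × 0.20 × 0.688 = 9.9 and 72 × 0.10 × 0.889 = 6.4.

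| Never start, control / intervention | Imputed control rate | Imputed intervention rate | Difference (true: 25.0) | Imputed eradications, control + intervention |
|---|---|---|---|---|
| 5% / 5% | 57.9% | 84.2% | 26.3 | 2.1 + 3.0 |
| 10% / 10% | 61.1% | 88.9% | 27.8 | 4.4 + 6.4 |
| 12% / 10% | 62.5% | 88.9% | 26.4 | 5.4 + 6.4 |
| 10% / 5% | 61.1% | 84.2% | 23.1 | 4.4 + 3.0 |
| 20% / 10% | 68.8% | 88.9% | 20.1 | 9.9 + 6.4 |
| 20% / 5% | 68.8% | 84.2% | 15.5 | 9.9 + 3.0 |
| 30% / 10% | 78.6% | 88.9% | 10.3 | 17.0 + 6.4 |

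**Step 4: direction.** Both arm rates always rise. The difference shrinks only when the control share c exceeds 1 − 0.55 / (0.80/(1 − i) − 0.25), where i is the intervention share. For i = 5% that is 1 − 0.55/0.592 = 7.1%; for i = 10% it is 1 − 0.55/0.639 = 13.9%. Below those values the difference grows, even when somewhat more controls than intervention participants never start.

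**The case against.** The strongest reply is that never-starters need not be missing at all. The outcome is confirmed eradication; without a qualifying test nothing is confirmed, so failure is a natural reading. Intention-to-treat and the failure rule point the same way. This stands as a reading, and the plan nowhere says that never-starters count as missing. But if every untested person is a failure by definition, the planned imputation has nothing to impute. The plan must intend some untested participants to be missing, and it does not say which.

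A second reply is that missing at random is conditional on observed data, and that adherence scales are collected and could enter the model. That helps for people who started. It does little for never-starters: hardly any untreated people will have a test, so the data hold almost nothing from which to learn their rate. Their outcome is better set by definition.

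A reader might also infer more than the documents support:

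- **That the primary result is compromised.** It is exposed only through the undefined notion of loss to follow-up. Dropping never-starters would contradict the intention-to-treat statement.
- **That the bias always runs against the intervention when more controls never start.** Step 4 shows otherwise: 12% / 10% gives 26.4 points.
- **That each never-starter is imputed as eradicated.** Each receives a probability of eradication.
- **That the trial loses power.** At 20% / 5%, the imputed rates give 59% with 72 per arm, but that treats imputed values as observed; on the roughly 58 and 68 observed participants it is about 54%. Neither is a design quantity, because the trial is sized on the primary test.

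**Conclusion.** The gap is real and confined mainly to the sensitivity analysis. The window is tied to treatment, no rule covers an untested never-starter, and imputing such a person under missing at random gives about the treated patients' chance of eradication. Over the assumed shares, the imputed difference runs from 10.3 to 27.8 points against a true 25, with about 5 to 23 eradications among 144 credited to untreated people. The effect is small at low, similar shares and large only with a marked imbalance between arms.

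These sizes rest on the assumed shares, on never-starters being treated as missing, and on a simple within-arm model. The sample size, the primary test and the stated power do not change. The text is underspecified rather than wrong as written; the point is a cheap improvement to the sensitivity analysis.

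**What to change.** In III.B1, state for both the primary and the imputation analyses that a randomised participant known not to have started the eradication course is scored as not eradicated, unless a valid test shows otherwise. The exception keeps an observed result from being overridden. It needs a time frame counted from randomisation, since the post-treatment window cannot apply.

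Restrict imputation to participants without a valid test who started the course or whose start is unknown, so that incomplete recording is not taken as non-treatment. Put adherence in the imputation model. Define loss to follow-up, and report never-starters by arm.

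The cost is one treatment-start variable. The EHR fields listed in III.A2 do not name one, but that section already uses the EHR to follow treatment outcomes, and the 2-month survey could ask. No change to the sample size or to patient care is involved.

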B9. Substudy Background. Gastric cancer is usually incurable when diagnosed at an advanced stage. About four out of five stomach cancers in the United States are diagnosed after the cancer has spread to other areas of the body, with the five-year survival rate at 4 percent¹⁰⁵⁻¹⁰⁷. Since there is no standard or routine screening test for gastric cancer in the US, it is therefore critical to develop novel biomarkers to improve prevention, risk assessment and early detection among Chinese Americans. This substudy aims to evaluate the feasibility and response rate for the collection of biosamples among Chinese Americans with a clinically confirmed diagnosis of *H. pylori*. The biosamples will be used to assess differences in oral and gut microbiome profiles before and after *H. pylori* antibiotic therapy.

C. Study Design

C1. Overall Design

The purpose of this study is to implement and test the relative effectiveness of an integrated *H. pylori* test-and-treat EHR-CHW intervention among Chinese American patients compared with usual care of EHR-only intervention. The primary outcome of interest is *H. pylori* eradication. The secondary outcomes of interest are *medication adherence, self-efficacy, health literacy and other factors*. This stomach cancer prevention study will use a 2-arm RCT design to evaluate the efficacy, adoption, and impact of an integrated EHR-based decision-support intervention with CHW-led coaching for high-risk Chinese American patients to achieve optimal adherence to *H. pylori* eradication medication regimen. An advisory group will guide the development of a user-friendly EHR intervention and culturally adapted materials relevant for Chinese Americans. The interventions will be collaboratively developed and implemented in NYC safety net hospitals and clinic sites that serve large proportions of Chinese American patients.

In Year 1, we will engage in a collaborative effort to develop and refine an evidence-based clinical decision-support and physician feedback mechanism that can be integrated into existing EHR systems. In

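### Secondary hypothesis 2 concerns self-efficacy for adherence, but the only self-efficacy instrument documented is a decision self-efficacy scale, so as documented the comparison cannot support a conclusion about adherence self-efficacy

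*Combined protocol and SAP*

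**What the plan says.** Section III.B1 lists the secondary hypotheses. Compared with usual care, the intervention group "will report: 1) increased medication adherence; 2) increased self-efficacy for adherence; 3) improved health literacy", followed by knowledge and quality of life. These intermediate outcomes are to be compared between arms by t-test or Wilcoxon rank-sum test.

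Section C2 of the study design sets out the measures. Its secondary outcomes "include: self-efficacy, health literacy, medication adherence and other factors". On the instrument it says: "Self-efficacy will be measured by the Ottawa Decision Self-Efficacy Scale". Section C1 uses the same unqualified label in its own list: "medication adherence, self-efficacy, health literacy and other factors". The words tying self-efficacy to adherence appear only in III.B1.

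Section III.A1 describes the community health worker sessions: "session 1 will focus on medication adherence, treatment side effects, and the link between" the infection and stomach cancer. The materials, informed by Social Cognitive Theory, are to review "individualized challenges, strategies and action plans for medication adherence and stomach cancer prevention".

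**The concern.** A hypothesis and the instrument that tests it should concern the same construct. Confidence in taking a multi-drug regimen as prescribed and confidence in making a health decision are different things to ask a patient about, and the first can change without the second. If the plan is followed as written, hypothesis 2 will be judged on a scale named for the second.

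What is at stake is the wording of the conclusion. A null result could be read as showing that the intervention does not raise confidence in adhering, although no documented instrument asks about that. A positive result would support a statement about decisions, not about adherence. The protocol says its secondary analysis is partly guided by Social Cognitive Theory, so readers are likely to use this result to explain how the programme works, and others may rely on it when replicating the programme.

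**Working it through.** The question is whether construct and instrument match, so the check sets the sections side by side.

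**Step 1. Match each hypothesis in III.B1 to the instrument named in C2.**

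| Hypothesis (III.B1) | Instrument named (C2) | Match by name |
|---|---|---|
| 1. Medication adherence | SMAQ and MARS-5 | Yes |
| 2. Self-efficacy for adherence | Ottawa Decision Self-Efficacy Scale | No: the scale names decisions |
| 3. Health literacy | HLS-EU-Q12 | Yes |
| 4. Stomach cancer prevention knowledge | None named | Cannot be judged |
| 5. Health-related quality of life | PROMIS Global Health | Yes |

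Every other named scale is assigned to another construct, so none can be read as the intended measure for hypothesis 2. SMAQ and MARS-5 measure adherence itself, not confidence in adhering.

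**Step 2. Look for a bridge.** Every mention of self-efficacy was checked. No section says that the decision scale is adapted to medication-taking, validated for it, or used as a proxy. C2 gives three criteria for choosing measures: brevity, face validity for the communities concerned, and psychometric quality. Match to the hypothesised construct is not among them.

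**Step 3. Check what else is affected.** The plan gives no power figure for self-efficacy. Its only power statement is for eradication (III.B1): 55% against 80%, 144 participants randomised evenly, two-sided 0.05, more than 80% power. With 144 / 2 = 72 per arm and a pooled proportion of (0.55 + 0.80) / 2 = 0.675:

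- Standard error under the null: √(2 × 0.675 × 0.325 / 72) = 0.0781
- Standard error under the alternative: √((0.55 × 0.45 + 0.80 × 0.20) / 72) = 0.0752
- Power: Φ((0.25 − 1.960 × 0.0781) / 0.0752) = Φ(1.29) ≈ 90.1%

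A continuity correction gives 86.5% and Fisher's exact test 87.0%. The plan's statement is reproduced, and the choice of self-efficacy instrument does not enter it.

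For context, assuming complete follow-up of 72 per arm, the difference detectable with 80% power on any secondary scale is (1.960 + 0.842) × √(2/72) = 0.47 standard deviations. That is the same for either type of scale. The problem is which construct is measured, not precision.

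**The case against.** **The surveys are not reproduced.** Appendices F and G are listed only by title, and both C1 and C2 leave the outcome list open-ended. C2 is also not a full inventory, since it names no instrument for hypothesis 4 (knowledge). Silence in C2 is therefore weak evidence about what the surveys contain. This stands. A reader might infer that hypothesis 2 cannot be answered at all, but the documents support only the narrower statement that it cannot be answered by the instrument as documented. For the same reason, counting how many of the five hypotheses lack an instrument would say more than the documents allow.

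**The argument rests on the scale's name.** This also stands in part. The items are not in the documents, so how strongly the scale would respond to adherence coaching cannot be judged. The mismatch in the text remains, because the plan offers nothing to link the two constructs.

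**Decisions may be relevant to these patients.** Registry patients are identified within 7 days of diagnosis, and no inclusion criterion requires that treatment has been accepted or started. Background section B7 lists preference for traditional medicine and lack of information about side effects among reasons for nonadherence. A reader might infer that the sessions involve no treatment choice, but the documents do not rule one out. This could justify measuring decision self-efficacy. It does not turn the scale into a measure of confidence in adhering, and the protocol does not offer this rationale.

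**No mediation analysis is planned.** A reader might infer that a planned causal chain from coaching through self-efficacy to adherence and eradication has lost a link. The protocol states no such chain. It says only that the secondary analysis is guided in part by theory, and it compares intermediate outcomes between arms.

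**The consequence is small.** This is a secondary outcome without a power statement, and adherence is measured directly. That limits the importance of the point but does not remove it.

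**Conclusion.** The point holds in a limited form. Hypothesis 2 is worded for self-efficacy for adherence, and the one documented instrument is named for decision self-efficacy, with no adaptation or justification recorded. As documented, the between-arm comparison on that scale supports no conclusion, positive or null, about self-efficacy for adherence.

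It affects what may be claimed from one secondary outcome. No bias can be quantified, and eradication, the sample of 144 and the primary power are untouched. The conclusion rests on two assumptions: that the scale measures what its name says, and that the unreproduced surveys contain no separate adherence self-efficacy items. If the second is wrong, the gap is one of documentation and naming the measure closes it.

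**What to change.** Before results are known, reword hypothesis 2 in III.B1 to *increased decision self-efficacy*, and make no claim about self-efficacy for adherence in reports. This is a one-line edit with no effect on data collection.

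If the surveys in Appendices F and G already contain an adherence self-efficacy measure, name it in C2 and analyse hypothesis 2 on it instead. That also costs only text.

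Adding a new scale now is less attractive. Section VI.G refers to participants who consented under previous protocol versions, so some would have no baseline value. The scale would also need translation and would have to meet C2's own selection criteria. In addition, the follow-up surveys fall at 2 and 6 months, whereas the guideline course described in B5 lasts 14 days, so a new scale might largely capture confidence after treatment has ended.
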